Since this is a pilot sub-study carried out with a limited number of subjects after completion of the main 12 week study, we have adopted a unilateral exercise protocol in which the resting contralateral limb serves as a control. This protocol will allow us to gain considerable insight into the salutary molecular processes activated by exercise in ESRD subjects and to test whether these processes can be enhanced by provision of a leucine-rich supplement. In brief, two to three days after completing the primary 12-week study, subjects from both the exercise and usual care groups will be studied in which one limb is exercised for 15 minutes, after which the vastus lateralis muscles of both the exercised and the contralateral resting limb will be biopsied. *Half the subjects in each of these 2 main groups (12 subjects from each group) will be matched by BMI and age and randomized to either a placebo mixture or a high calorie nutrient supplement.* The nutrient supplement will consist of a high-calorie leucine-rich protein (whey protein) given at the start and end of the exercise session. The study consists of the following 4 groups, each undergoing acute, unilateral exercise:

- Group 1.** Regular exercise group plus placebo
- Group 2.** Regular exercise group plus nutrient supplement
- Group 3.** Usual care group plus placebo
- Group 4.** Usual care group plus nutrient supplement

An outline of the experimental protocol is illustrated in Figure 2, and a detailed protocol follows.

[figure not shown]
Figure 2. Acute Exercise, Muscle Biopsy, and Nutrient Supplement Protocol for Specific Aim 2

Biopsies will be obtained from the dominant limb after acute exercise and from the non-dominant limb following rest. A *single* biopsy of each limb will be taken from each subject. Tissue taken from the biopsies will undergo molecular analysis to answer the following questions:

[figure not shown]

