1. What sustained molecular processes, activated by regular exercise, might be contributing to the maintenance or improvement of muscle mass in MHD subjects who participate in a 12 week exercise program? To this end, molecular events in the *resting* dominant limb of participants given placebo in regularly exercised (Group 1) and usual care (Group 3) subjects will be compared. We will test the postulate that regular exercise acts largely by inducing local changes in the expression of key regulators of muscle mass and also by stimulating the Akt/mTOR signaling pathways that serve to promote protein synthesis and inhibit proteolysis. We anticipate that a 12-week program of rehabilitation will increase muscle mass as measured by CT and DEXA scans, and improve skeletal muscle function via several interrelated mechanisms. These include changes in the balance between IGF-1 and myostatin, increased androgen receptor expression, changes in expression of components of the ubiquitin-proteasome and calpain proteolytic systems, suppression of inflammatory cytokines, and increased anabolic signaling. This is illustrated in Figure 3.

Figure 3. Assessment of 12 weeks of exercise training vs. usual care in resting muscle among subgroups receiving placebo.

2. What impact does acute exercise have on anabolic signaling in regular exercise versus usual care subjects? To answer this question we will measure activity (phosphorylation) of the IRS-1/AKT and mTOR signaling transduction pathways in the *acutely exercised* (and the contralateral resting) limbs of regular exercised subjects ingesting placebo (Group 1). The same measurements will be made in the muscle of the corresponding usual care group (Group 3) (Figure 4). Activity of the anabolic IRS-1/AKT and mTOR signaling pathways in the exercised limb will be compared with these responses in the contralateral resting limb of the same subject. We anticipate that acute exercise will activate anabolic signaling in both groups and that the response will be more vigorous in the regular exercise group.

[figure not shown]
Figure 4. Assessment of the response to acute exercise in trained vs. usual care subjects

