3. Does ingestion of a high-calorie leucine-rich protein (whey) supplement enhance acute exercise-stimulated anabolic signaling? (Specific Aim 2A). The effect of a nutritional supplement on acute exercise-induced signal transduction will be assessed by comparing IRS-1/AKT and mTOR signaling in a unilateral acutely exercised limb of regularly exercised subjects ingesting the supplement (Group 2) versus the acutely exercised limb of comparable subjects ingesting placebo (Group 1). A similar comparison will be made between the exercised limbs of usual care subjects ingesting the supplement (Group 4) versus placebo (Group 3) (Fig 5).

We anticipate that the leucine-rich supplement will enhance the acute exercise-stimulated mTOR signaling pathway and that the response will be more marked in the group undergoing the 12 week exercise program. This thesis is based on reports that in healthy young subjects, a leucine-rich supplement added to a resistance exercise program stimulates muscle protein synthesis, mass and strength (64; 72) and although delayed in the elderly, the anabolic response is effectively stimulated by this regimen (73). In this regard, Hulmi reported that whey protein enhanced exercise-induced signal transduction (phosphorylation of p70S6K) by nearly five-fold over exercise alone in young healthy subjects (71).

Figure 5. Assessment of the effect of nutrient supplementation on the response to acute exercise.

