In summary, we anticipate that a 12-week program of exercise rehabilitation will increase muscle mass and improve skeletal muscle function and that this is mediated by several different processes that we aim to identify. In this regard we expect that basal anabolic signaling will be higher in the resting muscle of the regular exercise group versus the resting muscle of the usual care group, *a potential carry over effect of regular exercise*. In addition, we anticipate that while the high calorie whey supplement will cause an increase in anabolic signaling in the resting muscle of both groups, the response will be greater in the regular exercise group, *again possibly reflecting a carryover effect of regular exercise*. *If a carryover effect is indeed present, then this would support the hypothesis that regular exercise is beneficial even in ESRD*. We also anticipate that acute exercise alone will increase anabolic signal transduction, and that this response will be enhanced by the high calorie whey supplement. If true, **this holds the prospect of developing a simple therapeutic strategy to boost the anabolic response to regular exercise and thereby enhance the functional and cardiopulmonary benefits of exercise in patients with ESRD**.

Detailed Protocol for Nutrient Supplementation, Acute Exercise, and Biopsy for Specific Aim 2. An outline illustrating the acute exercise, biopsy, and nutrient supplementation protocol for Specific Aim 2 is presented in Figure 2. On a morning the day before regular MHD and after an overnight rest, both regular exercise and usual care subjects will consume a light protein-free breakfast between 7 and 8 am and will be studied three hours later after a 60-min rest. Subjects in both groups will then begin a unilateral dominant lower limb exercise session lasting \approx 15 min, with the contra-lateral limb at rest. At the start of the exercise session, subjects will ingest half the high calorie whey or placebo so as to compensate for AA deficiencies common in MHD subjects. The other half of the supplement will be ingested at the end of the exercise session so as to enhance anabolic signal transduction. This will be followed by 60 minutes of rest, then muscle biopsies will be performed on both limbs to assess anabolic signal transduction.

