Secondary analyses, Specific Aim 2. In this specific aim we will analyze molecular changes in muscle biopsied at baseline and at the end of the study. IGF-1 is a key muscle growth factor; Kopple et al (45) reported that IGF-1Ea mRNA levels rose ~100% in 12 MHD subjects undergoing 21.5 weeks of combined resistance and endurance exercise. We plan to compare changes in IGF-1 mRNA levels from baseline to those levels at the end of 12 weeks of rehabilitation or usual care. Muscle will be obtained from limbs at rest in the exercise and usual care subjects as described above (n=12/group) and we will consider a 50% change in IGF-1Ea mRNA to be a clinically meaningful difference. While there are no data available in MHD subjects to estimate the standard deviation of the change in these molecular indices from baseline, Appendix VIII may be used to estimate the power associated with an assumed standardized effect size that is small (0.3), medium (0.5) or large (0.8).

Secondary analyses, Specific Aim 2A. In this specific aim we will assess the nutrient-enhanced exercise-induced protein signal transduction pathway in subjects undergoing exercise versus usual care. Specifically, we will compare the change in activity (phosphorylation) of the mTOR signal transduction pathway induced by unilateral exercise alone versus unilateral exercise plus nutrient supplementation. This will be a pilot study of 12 subjects in each group. Since this is a novel measurement and there are no data in MHD subjects describing the variance of this response, a power analysis has not been carried out. Change in activity will be taken to equal the difference in activity between the unilateral exercise limb and the contra-lateral resting limb of the same subject. We will also examine the effect of the supplement alone vs. placebo on signal transduction in the resting limb of unilateral exercise and usual care subjects. Of note, Hulmi (71) reported that whey protein enhanced exercise-induced signaling (phosphorylated p70S6K)

by nearly 5-fold over exercise alone in young healthy subjects, while Drummond (73) noted a similar increase in the elderly following EAA ingestion.

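### Under the stated limb rule, the within-subject acute-exercise effect cannot be told apart from a dominant versus non-dominant limb difference; balanced random limb assignment would remove this at modest cost.

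*Combined protocol and SAP*

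**What the plan says.** Section B, Approach to Specific Aim 2, uses the contralateral leg as the resting control and fixes the side: "Biopsies will be obtained from the dominant limb after acute exercise and from the non-dominant limb following rest". It adds: "A *single* biopsy of each limb will be taken from each subject". The detailed protocol for supplementation, acute exercise and biopsy agrees: "Subjects in both groups will then begin a unilateral dominant lower limb exercise session lasting" about 15 minutes, with both legs biopsied after an hour's rest.

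The comparisons built on these samples are:

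- **Question 1:** resting muscle, Group 1 versus Group 3. Here the plan refers to "molecular events in the *resting* dominant limb of participants given placebo in regularly exercised (Group 1) and usual care (Group 3) subjects", a sample that the rule above does not supply.
- **Question 2:** activity "in the exercised limb will be compared with these responses in the contralateral resting limb of the same subject". Activation is expected in both training arms, and more strongly in the trained arm.
- **Question 3 and Aim 2A:** supplement versus placebo, in the exercised limb or in a response defined as "the difference in activity between the unilateral exercise limb and the contra-lateral resting limb of the same subject".

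No section randomizes the limb or explains why it is fixed. The Statistical analysis plan's model for Specific Aim 2 contains period, treatment and their interaction, with no limb term.

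**The concern.** A contralateral control works when the two limbs differ only in the condition under study. Here they also differ in dominance, in the same direction for every subject. If dominant and non-dominant muscle differ at rest in phosphorylation or expression, the exercised-minus-resting difference contains that gap, and more subjects will not shrink it.

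At stake is the Question 2 statement that acute exercise activates signaling in each arm. The plan's own rationale makes a resting gap conceivable. It describes mechanical load as acting locally on IGF-1 and Akt/mTOR, and it expects a carryover of training into resting muscle. By that reasoning a more-used leg could sit higher at rest, which would push toward the predicted result. This is an inference from the rationale; the documents report no such gap.

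**Working it through.** **Inputs.** The limb rule and the single biopsy per limb come from section B and the detailed protocol. Group size is 12 under Secondary analyses, Specific Aim 2A. Section B can also be read as 12 per training arm split between supplement and placebo, which gives 6 per group, so both are shown. The plan states no power or significance level for this contrast, so there is no figure to reproduce. A two-sided 5% test is assumed. The dominance difference is not given and is assumed over a range.

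**1. Within-subject contrast.** Let D = exercised − resting = θ + δ + e, where θ is the acute exercise effect, δ is the dominant-minus-non-dominant difference, and both are in units of SD(D). Under the fixed rule the mean of D estimates θ + δ. With one post-exercise sample per limb, θ and δ cannot be estimated separately.

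**2. Rejection rate when θ = 0.** The paired t statistic is noncentral t with n − 1 degrees of freedom and noncentrality δ√n. For n = 12 and δ = 0.5, the noncentrality is 0.5 × √12 = 1.73.

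| δ (assumed) | n = 12 | n = 6 |
|---|---|---|
| 0.2 | 9.7% | 6.9% |
| 0.3 | 15.8% | 9.3% |
| 0.5 | 35.3% | 17.1% |

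Simulation with 50,000 runs agrees for δ = 0.3 and 0.5 (15.8% and 35.2% at n = 12; 9.2% and 17.1% at n = 6). The rates are lower at n = 6 only because the test is weaker; the bias is δ in both columns.

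**3. Between-group contrasts.** Every group follows the same limb rule. The difference between two groups' mean D is (θ₁ + δ) − (θ₂ + δ) = θ₁ − θ₂, so a common δ cancels. Single-limb comparisons use the same side in both groups, and δ cancels there too. Simulated type I error for the difference of differences is 4.9% to 5.3% (δ = 0.3, 0.5, 0.8; n = 6 and 12).

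**4. Balanced random limb, with a limb term.** Now D = θ + sδ + e, with s = +1 if the dominant limb is exercised and −1 otherwise, split equally within each group. The mean of D estimates θ, and the limb term is orthogonal to it, so only one degree of freedom is lost.

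| Contrast (assumed effect) | Fixed limb | Balanced, limb term |
|---|---|---|
| Paired, n = 12 (0.8 SD, δ = 0) | 71.4% | 70.5% |
| Paired, n = 6 (0.8 SD, δ = 0) | 35.6% | 32.5% |
| Between groups, 12 each (1.0 SD) | 64.9% | 64.7% |

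**5. If the limb term or the balance is left out.** Without the term, sδ enters the residual and the SE of D grows by about √(1 + δ²), which is 1.04, 1.12 and 1.28 for δ = 0.3, 0.5 and 0.8. Between-group power then falls from 64.9% to about 61.1%, 55.4% and 44.8%. Without balancing, the chance of a 75/25 or worse limb split in a group is 14.6% at n = 12 and 21.9% at n = 6.

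**The case against.** The best defense is that a fixed limb keeps the between-group contrasts homogeneous, and most of Aim 2 consists of such contrasts: Question 1, the arm comparison in Question 2, and Question 3 with Aim 2A. This stands. A reader might infer that the whole sub-study is confounded. The documents do not support that, because all groups share one limb rule and a common dominance difference cancels. Training could in principle change the difference in one arm, but nothing in the documents says that it does.

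Second, the size is entirely assumed. The rejection rates require no exercise effect at all together with a real dominance gap. A reader might conclude that a positive result would probably be spurious; the documents cannot show that, and the gap could be small beside the exercise response.

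Third, baseline biopsies exist and might include the dominant limb at rest. Their side is not stated and they precede the acute session by 12 weeks, so they do not reliably separate the two effects.

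Fourth, randomizing the limb is not free. It adds dominance variation to contrasts that now have none, including the single-limb comparisons, unless those are adjusted. The thigh CT is done on the non-dominant limb, so about half of the resting biopsies would no longer come from the scanned leg. Both costs are real. The first is nearly removed by balance and a limb term, and no stated analysis depends on the second.

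Finally, this is a pilot serving secondary endpoints, and the primary endpoint, peak VO₂, is untouched. That limits the urgency.

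**Conclusion.** The concern holds for one contrast. Under the rule in section B and the detailed protocol, the within-subject acute-exercise effect is aliased with limb dominance, and the planned analyses do not separate them. The bias equals the dominance difference, whose size the documents do not give. The rejection rates above, up to 35.3% at 12 per group for 0.5 SD, illustrate what an assumed gap would do and do not estimate what will happen. The between-group contrasts are unbiased provided the gap is the same in all groups. Separately, Question 1's reference to a resting dominant limb contradicts the limb rule and has to be reconciled whichever design is kept. This is a worthwhile, inexpensive improvement to a pilot sub-study and does not threaten the main trial.

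**What to change.** 1. Have the independent third-party assigner, who already allocates supplement or placebo, also allocate the exercised limb at random, balanced between dominant and non-dominant within each of Groups 1 to 4. Do this before the separate-day unilateral 1-RM test, so that the test is done on the assigned limb.
2. In section B and the detailed protocol, replace dominant and non-dominant by assigned and contralateral limb. In Question 1, refer to the resting contralateral limb.
3. State which limb is biopsied at baseline.
4. Fit a limb-dominance term in every affected analysis: the exercised-minus-resting differences, the single-limb comparisons of Questions 1 and 3, and the baseline-to-12-week change.

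The cost is one more entry on the assignment list, an earlier assignment step, one degree of freedom per model (paired power 71.4% to 70.5% at n = 12, or 35.6% to 32.5% at n = 6, for the assumed 0.8 SD effect), and loss of the match with the CT limb in about half of the subjects. No biopsy, visit or subject is added.

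If the sponsor keeps the limb fixed, the protocol should give its reason, correct Question 1, and limit acute-exercise conclusions to the between-group contrasts.

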Specific Aim 2. To elucidate the mechanisms whereby a program of exercise-based rehabilitation counteracts muscle wasting in elderly ESRD patients.

Specific Aim 2A. To determine whether the mTOR anabolic signaling response to exercise or a high-calorie leucine-rich protein load is intact in elderly MHD patients and whether the response to exercise is enhanced by providing this supplement at the time of exercise.

Hypotheses:

Hypothesis # 1. Regular exercise, by counteracting muscle wasting, enhancing cardiopulmonary and muscle function, and reducing cardiac risk factors, will improve muscle mass, cardiopulmonary function, and psychosocial health in elderly MHD patients. We anticipate that our approach to implementing a home-based rehabilitation program, modeled on a program effective in cardiac patients, in a rigorous randomized clinical trial will provide an innovative and relatively low-cost approach to the management of ESRD patients. It is our hope that this proposal will lead to future studies in which long-term outcomes of elderly MHD subjects will be improved.

Hypothesis # 2. The mechanisms whereby regular exercise counteracts muscle wasting in elderly ESRD patients are explained by changes in local skeletal muscle expression of IGF-1, androgen receptors and myostatin, and by stimulating Akt signaling pathways that promote protein synthesis and inhibiting proteolysis.

Hypothesis # 2A. Provision of leucine-rich protein at the time of acute exercise will stimulate skeletal muscle anabolic signaling in uremia. By augmenting exercise-induced signal transduction, this will increase the anabolic response to exercise.

Significance:

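### Aim 2A has two different stated contrasts for whether the supplement enhances the exercise response, and the plan does not say which one governs

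*Combined protocol and SAP*

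**What the plan says.** The Specific Aims section separates two matters. One is "To determine whether the mTOR anabolic signaling response to exercise or a high-calorie leucine-rich protein load is intact in elderly MHD patients"; the other is "whether the response to exercise is enhanced by providing this supplement at the time of exercise".

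The design section (B. Approach to Specific Aim 2) explains that "we have adopted a unilateral exercise protocol in which the resting contralateral limb serves as a control". Each of the four groups (trained or usual care, placebo or supplement) exercises one leg, and both legs are biopsied.

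Two places then say how the supplement question will be answered.

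- **B. Approach to Specific Aim 2, question 3.** The stated method is "comparing IRS-1/AKT and mTOR signaling in a unilateral acutely exercised limb of regularly exercised subjects ingesting the supplement (Group 2) versus the acutely exercised limb"; this second limb belongs to Group 1, who take placebo. Groups 4 and 3 are compared in the same way. The resting limb does not enter. The text predicts a stronger response in trained subjects.
- **Statistics, Secondary analyses, Specific Aim 2A.** Here "we will compare the change in activity (phosphorylation) of the mTOR signal transduction pathway induced by unilateral exercise alone versus unilateral exercise plus nutrient supplementation". The definition follows: "Change in activity will be taken to equal the difference in activity between the unilateral exercise limb and the contra-lateral resting limb", both limbs being from one person. A further analysis is added: "We will also examine the effect of the supplement alone vs. placebo on signal transduction in the resting limb".

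The summary after question 3 anticipates that "the high calorie whey supplement will cause an increase in anabolic signaling in the resting muscle of both groups", with the larger rise in the trained group.

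The Statistical analysis plan gives Aim 2 a linear model with period, training group and their interaction. It also assigns muscle-biopsy comparisons before and after the study period to multivariate ANOVA with Bonferroni post-hoc comparisons.

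**The concern.** Enhancement of the exercise response means that the supplement adds more in the exercised leg than in the resting leg. A comparison of exercised legs alone cannot show this when the supplement also acts at rest, and the plan expects it to. If question 3 is followed as written, a general nutrient effect could be reported as enhancement. The prediction of a stronger response in trained subjects could likewise be met by their larger resting response alone.

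The planned resting-limb comparison lessens the risk but does not remove it, because significance in one leg and not in the other is not a test of the difference between legs.

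What is at stake is the reading of a pilot. Item (7) of the limitations says a positive result will be the basis of a larger study.

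**Working it through.** The plan gives no effect size, variance, alpha or power for Aim 2A, so there is no planned figure to reproduce.

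**1. What each contrast estimates.** Let R be the resting level, E the exercise effect, S the supplement effect at rest and I the extra supplement effect in the exercised leg (enhancement), on an additive scale.

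| | Resting leg | Exercised leg |
|---|---|---|
| Placebo | R | R + E |
| Supplement | R + S | R + E + S + I |

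- Exercised legs only: (R + E + S + I) − (R + E) = S + I.
- Limb change: [(R + E + S + I) − (R + S)] − [(R + E) − R] = I.

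The two agree only if S = 0. Between trained (T) and usual-care (U) subjects, the first contrast differs by (S_T − S_U) + (I_T − I_U) and the second by I_T − I_U. The plan expects S > 0 in both groups and S_T > S_U.

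**2. Illustrative size.** Assumptions: two-sided t-test, I = 0, S in SD units. The 0.05 level is stated only for the primary endpoint. The sub-study's 12 per group can be read as 12 or 6 per cell, so both are shown. Probability that the exercised-limb contrast is significant (noncentral t):

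| S (SD) | 0.3 | 0.5 | 0.8 | 1.0 | 1.2 |
|---|---|---|---|---|---|
| 12 per cell | 11% | 22% | 47% | 65% | 80% |
| 6 per cell | 8% | 12% | 24% | 35% | 47% |

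The limb change rejects in about 5% throughout.

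**3. With multiplicity adjustment.** If the four proteins mTOR, p70S6K, rpS6 and 4EBP-1 are each tested in two training groups, there are 4 × 2 = 8 comparisons, and Bonferroni gives 0.05/8 = 0.00625. With 12 per cell, the rates at 0.5, 0.8 and 1.0 SD fall to 5%, 17% and 31%.

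**4. Reading the two legs side by side.** With I = 0, 12 per cell and limb correlation 0.5, simulation gives a significant exercised leg with a non-significant resting leg in 7.5%, 12%, 17%, 16% and 11% of trials for the five values of S (unadjusted 0.05).

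**5. Trained against usual care.** With assumed S = 1.0 SD in trained and 0.5 SD in usual-care subjects, and no enhancement in either, the exercised-limb contrast is significant in the trained group only with probability 0.649 × (1 − 0.216) = 0.51 (12 per cell), or 0.347 × (1 − 0.123) = 0.30 (6 per cell), again unadjusted.

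**6. Scale.** Suppose rest = 1, exercise multiplies by 3, supplement by 1.5, and the effects simply multiply. The arithmetic limb-change contrast is (4.5 − 1.5) − (3 − 1) = 1.0. On the log scale it is ln(4.5/1.5) − ln(3/1) = 0. Whether there is enhancement depends on the scale.

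**7. Precision.** The SD of the limb difference relative to one limb is √(2(1 − ρ)), which exceeds 1 when the limb correlation ρ is below 0.5. At 80% power and 12 per cell, the exercised-limb contrast detects a total effect of 1.20 SD. The limb change detects an enhancement of 1.69, 1.42, 1.20 and 0.93 SD at ρ = 0, 0.3, 0.5 and 0.7.

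**The case against.** The best reply is that the plan already contains the right analysis. The Statistics paragraph headed for Aim 2A defines the limb change, the design section makes the resting leg the control, and a resting-limb supplement comparison is planned. On this view question 3 is narrative, and only a cross-reference is missing. Most of this stands, and it is why the point is minor. It does not remove the conflict: question 3 states its own rule of assessment, and its pathways (IRS-1/AKT and mTOR) differ from those in the limb-change sentence (mTOR). Figure 5, which accompanies question 3, is not shown and might settle the matter.

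The plan also uses enhancement loosely, for whey plus exercise exceeding exercise alone. On that usage the exercised-limb comparison is a legitimate total effect. The aim's own wording favors the narrower meaning.

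A reader might infer that IRS-1/AKT has no resting-limb analysis for the supplement. The text does not support this: that analysis refers to signal transduction generally. What IRS-1/AKT lacks is an explicitly stated limb-change contrast for the supplement question.

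A reader might also take the missing limb and supplement terms in the Aim 2 model to mean that no method covers this contrast. The muscle-biopsy sentence with Bonferroni may cover it; whether it reaches this sub-study is unclear.

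**Conclusion.** The point holds as a contradiction between two stated analyses of one question. The exercised-limb contrast estimates the supplement effect plus enhancement; the limb change estimates enhancement alone on whichever scale is chosen. The Statistics version is probably the intended one, but no text available here says so.

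Two stronger readings are tempting. One is that the percentages are false-positive rates. They are not: they are power to detect a real total supplement effect, and they mislead only if that effect is called enhancement. They rest on assumed effect sizes and, unless adjusted, on a 0.05 level the plan does not set for this aim. The side-by-side and trained-only figures further assume a way of reading results that the plan does not prescribe. The other is that the limb change isolates enhancement unconditionally; the multiplicative example shows that it does not.

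Severity is minor. Aim 2A is an exploratory pilot with no power analysis, and the primary endpoint, peak VO2, is untouched.

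**What to change.** 1. In question 3, state that the answer comes from the limb change defined in the Statistics section, supplement against placebo within each training group (Group 2 vs 1, Group 4 vs 3), for mTOR and, as exploratory, for IRS-1/AKT.
2. In the same sentence, state whether the limb change is an arithmetic difference or a log-ratio.
3. Test the prediction of a stronger response in trained subjects by the supplement-by-training interaction on that limb change.
4. Label any exercised-limb-only comparison as the total supplement effect in exercised muscle, and keep the planned resting-limb analysis.
5. In the Statistical analysis plan, name the model and multiplicity rule for this contrast, for example limb change as outcome with supplement, training group and their interaction. Say whether the muscle-biopsy ANOVA and Bonferroni sentence applies.

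The cost is wording and one model statement, since both legs are already biopsied and both pathways already measured. There are two downsides. Precision is lost if the two legs correlate below 0.5. Adding IRS-1 and Akt raises the count from 8 to 6 × 2 = 12 comparisons if each protein is tested in both training groups. Results are best given as exploratory estimates with confidence intervals.
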